2.4.4.2.1 HbA1c $<7.0\%$ at Week 30 (yes/no)

Proportions of participants achieving the HbA1c target value of $<7.0\%$ at Week 30 will be compared by treatment group using a Cochran-Mantel-Haenszel (CMH) test stratified by randomization stratum of Screening HbA1c ($<8.0, \geq 8.0\%$) and Visit 3 (Baseline, Day 1) BMI ($<30, \geq 30 \text{ kg/m}^2$) in the ITT population. All HbA1c values at Week 30 will be used to determine whether a participant is a responder (HbA1c $<7.0\%$) or not, even if they are measured after IMP discontinuation or introduction of rescue therapy. Participants with missing HbA1c data at Week 30 will be considered not achieving HbA1c $<7.0\%$. The nominal p-value from the CMH test will be presented. No rounding for HbA1c will be done.

2.4.4.2.2 Changes from baseline in FPG to Week 30 and in body weight to Weeks 30 and 56 and in HbA1c to Week 56

Changes from Baseline in FPG to Week 30, in body weight to Weeks 30 and 56 and in HbA1c to Week 56 will each be analyzed by the same ANCOVA model with missing values imputed by MI method as described in [Section 2.4.4.1](#) the primary analysis. The least squares (LS) means, standard errors of LS means within each treatment group and the adjusted mean and associated two-sided 95% CI of the difference between efpeglenatide 2, 4, and 6 mg and placebo group will be presented.

Summary statistics at protocol scheduled visits and for the last on-treatment value will also be provided for FPG and body weight.

Additional Analysis

Analysis on completers at Week 30 (body weight)

For participants in ITT population who completed the 30-week core treatment period and did not start any rescue therapy before the end of the period, the secondary endpoint of change from Baseline in body weight to Weeks 30, will be assessed too by the same ANCOVA model as used for the primary analysis using the observed values.

Analysis on completers at Week 56 (HbA1c and body weight)

For participants in ITT population who completed the whole on-treatment period and did not start any rescue therapy before the end of the period, the change from Baseline in HbA1c and body weight to Weeks 56, will be assessed by the same ANCOVA model as used for the primary analysis using the observed values.

Sensitivity analysis due to COVID-19 at Week 56 (HbA1c and body weight)

Sensitivity analysis will be performed using ANCOVA (as specified in [Section 2.4.4.1](#)) with missing values imputed based upon retrieved dropouts, washout and MAR approach as described below, if there are more than 10 participants in total (regardless of treatment group) with missing endpoint data due to COVID-19. Participants with missing endpoint data due to COVID-19 are identified in Appendix C.

1. Missing endpoint data in participants who prematurely discontinue the study treatment before the Week-56 visit will be imputed using a model built separately in each arm and estimated from participants in the same treatment arm who prematurely discontinue the study treatment before the Week-56 visit but have the measurement for the endpoint (retrieved dropouts). Considering that the number of participants in each treatment arm who discontinue the study treatment but have the measurement for the endpoint is expected to be small, a simple imputation model will be used, where only the Hb1Ac/weight baseline measurements are included as the predictor. Each treatment group will have their own imputation model. Missing data will be imputed using the regression method.

2. a) Missing endpoint data not due to COVID-19 in participants in all groups, who stay on the study treatment until the Week-56 visit will be imputed using the washout-imputation method, where missing endpoint data in the efpeglenatide arms, as well as the missing data in the placebo arm, are imputed from a model estimated from participants in the placebo group with endpoint data without including any intermediate values. The imputation model will include the randomization strata and corresponding Hb1Ac/weight baseline values. Missing data will be imputed using the regression method.
b) Missing endpoint data due to COVID-19 in participants in each group, who stay on the study treatment until the Week-56 visit, will be imputed using separate models including the data at all scheduled visits within the same treatment group assuming missing at random.
 - Step 1: Use the Markov Chain Monte Carlo method in conjunction with the IMPUTE=MONOTONE option in PROC MI to create an imputed data set with a monotone missing pattern
 - Step 2: Based on the MONOTONE data sets obtained from Step 1, build the imputation model using the regression method sequentially for each scheduled visit. The imputation model will include the randomization stratum of Hba1c value at Screening ($<8.0, \geq 8.0\%$), the randomization stratum of Visit 3 (Baseline, Day 1) BMI ($<30, \geq 30 \text{ kg/m}^2$), corresponding baseline values and preceding scheduled postbaseline values.

Similar to what is specified in [Section 2.4.4.1](#), only Step 2 a) and b) will be applied if there are insufficient data to support the imputation approach in Step 1 above (ie, fewer than 5 participants in any arms who prematurely discontinue the study treatment before the endpoint visit but have the measurement for the endpoint).

Participants without data at the endpoint visit will be summarized by treatment status (discontinued, completed) and by impact of COVID-19 on participant (yes, no) for each treatment group.

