As noted, the number of retrieved dropouts is expected to be small, and there may not have sufficient data to support the imputation approach in item 1 described above. If there are less than 5 participants in any arms who prematurely discontinue the study treatment before the endpoint visit but have the measurement for the endpoint, a back-up imputation method for the primary efficacy analysis will be used. In particular, missing endpoint data in all participants in both efpeglenatide and placebo groups, regardless of staying on the study treatment or not, will be imputed using a model estimated from participants in the placebo group with endpoint data without including any intermediate values, where randomization strata and corresponding baseline values are included as the predictors. Missing data will be imputed using the regression method.

Sensitivity Analysis

Tipping point analysis

Tipping point analysis based on the same multiple imputation (MI) method as applied above will be performed to examine the robustness of the results from the primary analysis. A penalty δ will be applied to participants in the efpeglenatide group who have no HbA1C data at Week 30. The penalty will be gradually increased to determine at which level (if any) the conclusion of the

analyses in terms of statistical significance is changed for each efpeglenatide dose group. The tipping point is the penalty level at which the magnitude of efficacy reduction in participants without HbA1c data at Week 30 creates a shift in the treatment effect of efpeglenatide from being statistically significantly better than placebo to a non-statistically significant effect. The penalty δ will start at 0 and increase by 0.1 (unit: %) until non-statistical significance is found. Least square mean difference between each efpeglenatide dose and placebo and its associated p-value will be provided for each penalty level.

Analysis on completers

For participants in ITT population who completed the 30-week core treatment period and did not start any rescue therapy before the end of the period, the primary endpoint will be assessed too by the same ANCOVA model as used for the primary analysis using the observed values.

Assessment of missing data

The availability of primary and secondary efficacy data (yes, no) at the endpoint visit (Week 30 or Week 56) will be summarized by treatment status (discontinued, completed) and by treatment group.

Assessment of treatment effect by subgroup

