Appendix A Efficacy analysis SAS pseudo code

Primary Analysis missing data imputation:

1. Multiple imputations in participants who prematurely discontinued the study treatment before the Week-30 visit:

```
proc mi data= data_IN out= data_OUT_DISC n impute=10000 seed=14822;  
    where PEOTF30L = "Y";  
    by ARM;  
    var BASE AVAL_W30;  
    monotone regression (AVAL_W30= BASE );  
run;
```

2. Multiple imputations in participants who stay on the study treatment until the Week-30 visit

```
proc mi data= data_IN out= data_OUT_COMPL_MI n impute=10000 seed=14822;  
    where PEOT30FL='N' and (ARM='Placebo' or (ARM ne 'Placebo' and AVAL_W30 =. ));  
    class HbA1c strata BMI strata;  
    var HbA1c strata BMI strata base AVAL_W30;  
    monotone regression (AVAL_W30 = HbA1c strata BMI strata BASE );  
run;
```

3. Transform dataset of EFPEG participants who are under treatment at Week 30 visit with a collected endpoint to have 10 000 replications.

```
Data data_OUT_COMPL_EFPEG;  
Set data_IN (where=( PEOT30FL='N' and ARM ne 'Placebo' and AVAL_W30 ne .));  
n_imput=1;  
%do i = 1 %to 10 000;  
n_imput=n_imput+1;  
%end;  
run;
```

4. Combine multiple imputations from the three subsets of participants

```
Data  dataMI;  
set   data_OUT_DISC  
      data_OUT_COMPL_MI  
      data_OUT_COMPL_EFPEG;  
run;
```

Back-up plan:

```
Data  data_OUT_COMPL_EFPEG;  
Set   data_IN (where=( ARM ne 'Placebo' and AVAL_W30 ne .);  
n_imput=1;  
%do i = 1 %to 10 000;  
n_imput=n_imput+1;  
%end;  
run;  
  
proc mi data =data_IN out=data_OUT_MI nimpute=10000 seed=14822;  
  where ARM='Placebo' or (ARM ne 'Placebo' and AVAL_W30 =.);  
  class HbA1c_strata BMI_strata;  
  var HbA1c_strata BMI_strata base AVAL_W30;  
  monotone regression (AVAL_W30 = HbA1c_strata BMI_strata BASE );  
run;  
data  dataMI;  
set   data_OUT_MI  
      data_OUT_COMPL_EFPEG;  
run;
```

Sensitivity analysis (*If more than 10 missing endpoint data impacted by COVID-19*):

```
#3 DATA data_OUT_COMPL;  
      Set data_IN (where = (PEOTF56L='N' and W56_missing = "N"));  
      _imputation_=0;  
      do i = 1 to 10 000;  
      _imputation_=imputation_+1;  
      output;  
      end;  
run;
```

#1 Multiple imputations in participants who prematurely discontinued the study treatment before the Week 56 visit:

```
proc mi data= data_IN out=data_OUT_DISC nimpute=10000 seed=14822;  
      where PEOTF56L = "Y";  
      by ARM;  
      var BASE AVAL_W56;  

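### The back-up path of the Week 56 COVID-19 sensitivity analysis uses two steps limited to on-treatment participants, which conflicts with the SAP's own rule that participants who stopped treatment are included.

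*SAP*

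**What the plan says.** The passage is in SAP 2.4.4.2.2, under the sensitivity analysis due to COVID-19 at Week 56.

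- **Step 1** imputes participants who stopped treatment early, arm by arm, from retrieved dropouts in the same arm.
- **Step 2 a)** is the placebo-based washout model. It covers "Missing endpoint data not due to COVID-19 in participants in all groups, who stay on the study treatment until the Week-56 visit".
- **Step 2 b)** is own-arm imputation under missing at random. It covers "Missing endpoint data due to COVID-19 in participants in each group, who stay on the study treatment until the Week-56 visit".
- **Back-up.** If any arm has fewer than 5 retrieved dropouts, "only Step 2 a) and b) will be applied if there are insufficient data to support the imputation approach in Step 1 above". The sentence opens by likening this to Section 2.4.4.1.
- **The section referred to.** The back-up in SAP 2.4.4.1 uses one placebo-based model for "missing endpoint data in all participants in both efpeglenatide and placebo groups, regardless of staying on the study treatment or not". It has no COVID-19 branch.
- **Main Week 56 analysis.** The continuous secondary endpoints "will each be analyzed by the same ANCOVA model with missing values imputed by MI method as described in" Section 2.4.4.1.
- **Reporting.** Participants without endpoint data will be "summarized by treatment status (discontinued, completed) and by impact of COVID-19 on participant (yes, no").

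Appendix A has a block headed Back-up plan, written for Week 30 ("where ARM='Placebo' or (ARM ne 'Placebo' and AVAL_W30" missing) with no COVID-19 split. The COVID-19 block has no back-up variant.

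**The concern.** Step 1 is the only step that names participants who stopped treatment. Once it is dropped, neither remaining step covers them as worded, and nothing in the paragraph widens the scope of 2 a) or 2 b). The cross-reference points the other way, to a rule that covers everyone.

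This analysis is meant to show what happens to the Week 56 result when COVID-19 missingness is handled differently. If it also differs from the main Week 56 analysis in who is analyzed, a difference between the two cannot be read as the effect of COVID-19. The endpoints are HbA1c and body weight at Week 56, which the hierarchy tests at steps 8 to 13.

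**Working it through.** **The plan's own figure.** The only design figure is in SAP 1.3: 89% (96%) power for -0.5 (-0.6) with 100 per arm, SD 1.1 and two-sided alpha 0.05. The normal approximation gives 89.5% and 97.1%, and the noncentral t gives 89.2% and 97.0%, so the figures are reproduced to about one point. They are not in dispute. The check below borrows n, SD and the -0.6.

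**1. Where each participant goes.** I applied the Appendix A filters to every combination of arm (placebo, efpeglenatide), treatment status and Week 56 value. The result is the same in both arms. The observed-value dataset, for example, begins "Set data_IN (where = (PEOTF56L='N' and W56_missing", so it admits on-treatment participants only; 2a and 2b carry the same restriction.

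| Treatment | Week 56 value | COVID-19 block with Step 1 | Same block, Step 1 left out | Logic of the Week 30 Back-up plan |
|---|---|---|---|---|
| stayed on | observed | data_OUT_COMPL | data_OUT_COMPL | kept |
| stayed on | missing, not COVID-19 | 2a output | 2a output | placebo model |
| stayed on | missing, COVID-19 | 2b output | 2b output | placebo model |
| stopped | observed | data_OUT_DISC | none | kept |
| stopped | missing, not COVID-19 | data_OUT_DISC | none | placebo model |
| stopped | missing, COVID-19 | data_OUT_DISC | none | placebo model |

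With Step 1, all 12 combinations (6 rows, 2 arms) land in exactly one component of DataMI. Without it, the 6 combinations of participants who stopped land in none, including retrieved dropouts with an observed Week 56 value.

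**2. How likely the back-up path is.** The documents give no stopping or retrieval rates, so these are assumed: share stopping d, share of those with a Week 56 value r = 0.3, 0.5, 0.7, and 100 per arm. P(any of 4 arms has fewer than 5) = 1 - (1 - P(Bin(100, d·r) ≤ 4))^4.

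| d | r = 0.3 | r = 0.5 | r = 0.7 |
|---|---|---|---|
| 5% | 1.000 | 1.000 | 0.994 |
| 10% | 0.999 | 0.899 | 0.510 |
| 15% | 0.951 | 0.407 | 0.064 |
| 20% | 0.726 | 0.092 | 0.004 |
| 25% | 0.407 | 0.014 | 0.000 |

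These probabilities are conditional on the analysis being run at all, which needs more than 10 participants with COVID-19-related missing data.

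**3. Size of the literal reading.** Assume d = 15%, an on-treatment difference of -0.6 (the Week 30 planning value) and no effect after stopping.

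- Everyone kept: -0.6 × 0.85 = -0.51.
- Only those with missing values lost: -0.6 × 0.85 / (0.85 + 0.15r) = -0.570, -0.551, -0.534 for r = 0.3, 0.5, 0.7.
- All who stopped lost (15 per arm, 60 of 400): -0.60.

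A simulation (20,000 runs, SD 1.1, r = 0.5) gave -0.509, -0.550 and -0.599 in the same order, with SEs 0.158, 0.164 and 0.170. The largest shift is 0.09 / 0.158, about 0.6 SE, in favor of efpeglenatide.

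**4. Size of the question that the text leaves open.** Step 2 a) or 2 b) for participants who stopped and are missing because of COVID-19? Assume 11 to 80 participants with COVID-19-related missing data across 4 arms, 15% to 25% of them off treatment, and a contrast of 0.6 between the own-arm and placebo models. Low end: 11 × 0.15 / 4 = 0.41 per arm, shift 0.0041 × 0.6 = 0.0025. High end: 80 × 0.25 / 4 = 5 per arm, shift 0.05 × 0.6 = 0.03, about 0.2 SE.

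**The case against.** The strongest reply is that the SAP already says enough. The sentence opens with the reference to 2.4.4.1, whose back-up disregards treatment status. SAP 2.3.1.1 defines ITT as all randomized participants, and 2.4.4 and 2.5.4 use efficacy data collected after treatment was stopped. SAP 2.5.4 also sends values still missing to the multiple imputation of 2.4.4.1. Appendix A is labeled pseudo-code.

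Most of this stands. A reader might infer that the SAP has no rule at all for participants who stopped treatment, or that dropping them is one of the analyses it permits. The documents support neither: dropping them contradicts the ITT and data-use rules and the definition of DataMI, which is to hold every participant's observed and imputed data. A reader might also infer that the hierarchical Week 56 tests are compromised. They rest on the main analysis, whose back-up has no such gap.

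Two things remain. The wording of 2 a) and 2 b) still contradicts the rule that the paragraph points to, and no Week 56 code resolves it. And 2.4.4.1 has no COVID-19 branch, so it cannot say which step takes participants who stopped and have COVID-19-related missing data. The planned cross-tabulation has a cell for them, though that does not show it will be filled. The Appendix C diagram is not shown in the text available here; 2.4.4.2.2 cites it for identifying such missing data, not for how to impute them.

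**Conclusion.** The concern holds as a conflict of scope plus missing code. Followed word for word, the back-up path leaves participants who stopped treatment out of an ITT sensitivity analysis; the rest of the SAP says they belong in it.

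Severity is minor. The path needs two conditions: more than 10 participants with COVID-19-related missing data, and an arm with fewer than 5 retrieved dropouts. The move from -0.51 to as much as -0.60 illustrates the literal reading only. It rests on an assumed 15% stopping, a -0.6 on-treatment effect and none after stopping, and is not a forecast. It would seldom reverse a test, but it could make the sensitivity result look better than the main one for a reason unrelated to COVID-19. The question that is truly open, 2 a) or 2 b), is worth at most about 0.03 percentage points under the assumptions shown.

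**What to change.** In SAP 2.4.4.2.2, state that on the back-up path:

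- all observed Week 56 values are kept, on or off treatment;
- missing values not due to COVID-19 are imputed from the placebo model whatever the treatment status, as in the 2.4.4.1 back-up;
- participants who stopped treatment and have COVID-19-related missing data follow a step named in advance.

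For the last item, the placebo model stays closest to the main back-up analysis and is conservative for efpeglenatide. Own-arm imputation is also defensible, since SAP 2.4.4 regards COVID-19 missingness as probably missing at random and allows same-arm data to be used. Either will do if it is fixed beforehand.

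Add a Week 56 back-up block to Appendix A for HbA1c and body weight, without the PEOT56FL='N' restriction where it would exclude these participants, and with retrieved dropouts carried into DataMI. The cost is two or three sentences and one code block, with no new data.

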2.4.4.3 Multiplicity issues

To protect the family-wise error rate for the secondary endpoint, the adjustment for multiplicity of comparison will be applied.

For secondary endpoints, a step-down testing procedure will be applied. For the primary efficacy endpoint (change from Baseline to Week 30 in HbA1c), the 3 efpeglenatide doses will be tested in the order of 6 mg, 4 mg, and 2 mg. Once the primary endpoint is statistically significant at $\alpha=0.05$ (2-sided) for all 3 efpeglenatide doses, a hierarchical testing procedure will be performed to test the following study secondary efficacy endpoints by the following prioritized order:

1. HbA1c $<7\%$ at Week 30 for efpeglenatide 6 mg versus placebo (yes/no)
2. HbA1c $<7\%$ at Week 30 for efpeglenatide 4 mg versus placebo (yes/no)
3. Change from Baseline to Week 30 in body weight (kg) for efpeglenatide 6 mg versus placebo

4. Change from Baseline to Week 30 in body weight (kg) for efpeglenatide 4 mg versus placebo
5. HbA1c <7% at Week 30 for efpeglenatide 2 mg versus placebo (yes/no)
6. Change from Baseline to Week 30 in FPG (mmol/L, mg/dL) for efpeglenatide 6 mg versus placebo
7. Change from Baseline to Week 30 in FPG (mmol/L, mg/dL) for efpeglenatide 4 mg versus placebo
8. Change from Baseline to Week 56 in body weight (kg) for efpeglenatide 6 mg versus placebo
9. Change from Baseline to Week 56 in HbA1c (%) for efpeglenatide 6 mg versus placebo
10. Change from Baseline to Week 56 in body weight (kg) for efpeglenatide 4 mg versus placebo
11. Change from Baseline to Week 56 in HbA1c (%) for efpeglenatide 4 mg versus placebo
12. Change from Baseline to Week 56 in HbA1c (%) for efpeglenatide 2 mg versus placebo
13. Change from Baseline to Week 56 in body weight (kg) for efpeglenatide 2 mg versus placebo

Based on the hierarchical testing above, the testing will stop as soon as an endpoint for an efpeglenatide dose is found to be not statistically significant at $\alpha=0.05$ (2-sided). No multiplicity adjustment will be made on other secondary efficacy variables or the comparison of other efpeglenatide dose versus placebo than mentioned above.

2.4.4.4 *Exploratory efficacy analysis*

2.4.4.4.1 *HbA1c <7.0 % at Week 56 (yes/no)*

Proportions of participants achieving HbA1c target values of <7.0% at Week 56 will be analyzed by same approach described in secondary endpoint: HbA1c < 7% at Week 30.

2.4.4.4.2 *Change in FPG from baseline to Week 56*

Change in FPG concentrations from Baseline to Week 56 will be analyzed by same approach described in secondary endpoint: Change in FPG from baseline to Week 30.

2.4.4.4.3 *Changes in 7-point SMPG from baseline to Weeks 30 and 56*

The 7-point SMPG profile should be measured at the following 7 points: pre-breakfast and 2 hours post-breakfast, pre-lunch, 2-hour post-lunch, pre-dinner, 2-hour post-dinner, and at bedtime. Two hours postprandial (breakfast, lunch and dinner) is defined as 2 hours after the start of the meal. On days when 7-point profiles are done, fasting pre-breakfast SMPG will be considered as the first point of measurement, ie, “pre-breakfast” time point.

Normally, investigator can only record one entry in the eCRF. In case of multiple records per visit for some participants, the most complete one should be selected; in case of a tie, the one closest to the visit will be selected for analysis. Descriptive statistics and graphical presentations will be presented by treatment group over time at each visit and for each time point.

- **Changes in mean 24-hour SMPG from Baseline to Weeks 30 and 56**

The mean 24-hour SMPG (7-point profile) will be calculated as the mean of the plasma glucose values over the 7 time points. The daily average data will be calculated only if at least 4 plasma glucose values are available. Only available plasma glucose values will be used for the calculation. For example, if the available data are pre-breakfast, post-breakfast, pre-lunch, and pre-dinner, then the daily average will be calculated as (pre-breakfast + post-breakfast + pre-lunch + pre-dinner)/4.

Descriptive statistics and graphical presentations will be presented by treatment group over time.

- **Changes in prandial glucose excursion from Baseline to Weeks 30 and 56**

The prandial glucose excursion, defined as the change in plasma glucose value after each meal (breakfast, lunch, or dinner), will be calculated by subtracting the preprandial value from the postprandial value.

Prandial glucose excursion will be summarized by treatment group and over time. Additionally, graphical presentations will be provided as appropriate.

Rescue therapy used during the treatment period until Weeks 30 and 56 (yes/no)

Proportions of participants who used rescue therapy during the treatment period until Week 30 and Week 56 will be compared by treatment group using a CMH test stratified by the randomization stratum of Screening HbA1c ($<8.0, \geq 8.0\%$) and Visit 3 (Baseline, Day 1) BMI ($<30, \geq 30 \text{ kg/m}^2$) in ITT population.

Time to initiation of rescue therapy (weeks)

Time to initiation of rescue therapy is defined as the time from the date of randomization to the date of first rescue therapy in weeks. Participants who did not take any rescue therapy during the study will be censored at the date of study completion/discontinuation. The curve of the cumulative incidence of participants with rescue initiation will be estimated using Kaplan-Meier method by study treatment group.

Patient reported outcome

The Patient Qualitative Assessment of Treatment version 2 (PQATv2) is intended for the collection of participant-perceived benefit-risk of glucose-lowering treatment with efpeglenatide. The participants will be asked to complete it from home just before the on-site visits planned at Weeks 30 and 56. If a participant discontinues treatment with IMP during the treatment period, the participant will be asked to complete the PQATv2 at the time of discontinuation.

The analysis of participant-reported outcome (PRO) endpoints will be descriptive with no formal testing. For categorical data, frequency and percentage will be provided by treatment group and overall at scheduled visits. Participants' answers to the open-ended questions of PQATv2 (items #1, 3 and 5) will be analyzed qualitatively and quantitatively, as relevant, using appropriate data analysis software. The analysis method for the open-ended questions will be provided in a separately and the analyses results will not be included in the CSR.

Other exploratory analysis

- Analysis to investigate whether the HbA1c decrease depends on the decrease in weight will be assessed by scatter plots of HbA1c reduction versus weight loss. A cumulative distribution plot will be provided for each of changes in HbA1c and in body weight from Baseline to Week 30 and 56.
- Proportion of participants with HbA1c <7.0% at Week 30 and 56 with no severe or documented symptomatic hypoglycemia will be assessed by number of participants and percentage by treatment group.
- Analysis of change in weight as a function of baseline BMI will be assessed by descriptive summary statistics at scheduled visits, by baseline BMI categorization (<19, [≥19 to <25], [≥25 to <30], [≥30 to <40], ≥40 kg/m²) and by treatment group.
- Analysis of proportions of participants with 5% and 10% weight loss at Weeks 30 and 56 will be assessed by number of participants and percentage by treatment group.

